5.1. Statistical Definitions and Algorithms

5.1.1. Baseline

The last non-missing observation recorded on or prior to the first patch application of study drug will be used as the baseline observation for all calculations of change from baseline. Typically, baseline will be the value recorded on the Baseline visit (Randomization).

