10.2.2.1 Laboratory Safety Assessments

10.2.2.1.1 Laboratory Tests to be Performed

Samples for the following laboratory tests will be collected at the timepoints specified in the schedule of events (see **Section 17.1**).

Hematology:	Hemoglobin, hematocrit, red blood cell (RBC) count, RBC indices, mean corpuscular hemoglobin, mean corpuscular hemoglobin concentration, platelet count (or estimate), white blood cell count including differential.
Serum chemistry:	Albumin, total bilirubin, direct bilirubin, total protein, calcium, alkaline phosphatase, alanine aminotransferase, aspartate aminotransferase, blood urea nitrogen, creatinine, fasting glucose and total lipids [8 to 10 hours after fasting is required for these laboratory testing], cholesterol, triglycerides, high density lipoprotein, sodium, potassium, chloride, bicarbonate, lactate dehydrogenase, uric acid.
Urinalysis:	pH, specific gravity, blood, glucose, protein, ketones, leukocyte esterase, nitrite, total bilirubin, urobilinogen.
Pregnancy test (urine):	For women of childbearing potential only.
Urine drug screen:	Amphetamines, barbiturates, benzodiazepines, cocaine, opiates, methamphetamine, methadone, phencyclidine, and tetrahydrocannabinol.
Alcohol test (urine):	Ethanol.

A central laboratory will be used to process all hematology, clinical chemistry, urinalysis samples. Urine drug screens and alcohol tests pregnancy tests will be conducted at the study sites. Details on sampling, handling, and storage of samples will be given in a separate laboratory manual.

Note: Female subjects (of childbearing potential) will undergo a urine pregnancy test at Screening (Visit 1) and at every subsequent visit.

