13.1.3 Safety Endpoints

- Adverse events, AEs leading to discontinuation from the study drug, SAEs, and deaths.
- Change from Baseline in clinical laboratory results (including fasting glucose and total lipids [8 to 10 hours after fasting is required for these laboratory testing]), ECG results, body weight, and vital signs.
- Dermal safety: adhesion, irritation, discomfort, and adhesive residue.

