- d. Rescue medication may be used during the Washout Period except within 2 calendar days prior to Visit 2 and within 1 day prior to each subsequent visit.
- e. A standard 12-lead electrocardiogram (ECG) will be performed after the subject has been supine for at least 5 minutes.
- f. Clinical laboratory testing includes hematology, biochemistry, and urinalysis. Results from laboratory testing done at Screening Visit will be used for confirmation of subject eligibility at Baseline Visit.
- g. Fasting glucose and lipids should be performed after 8 to 10 hours of fasting. Subject must be instructed to fast for 8 to 10 hours (no food or drink, except for water) before coming for the Baseline assessments, if not done at Screening.
- h. Subjects will be instructed on how to use of the electronic diary (eDiary) at the Screening Visit. For each 28-day administration period, subjects will be asked to record their NRS score, their intake/use of study drug and rescue medication in the eDiary.
- i. Study treatment will be applied on Day 1 of the Double-blind Treatment Phase. Instructions for application and removal of study drug patches will be provided to the subject at the Baseline Visit (V2).
- j. Dermal evaluations will assess skin adhesion, irritation, discomfort, and adhesive residue.
- k. Screening/Washout Period should be up to 28 days. Washout Period can be initiated 3 days after Screening Visit.

- l. During the Double-blind Treatment Phase, subjects will report the incidence of patch detachment by answering Yes or No and will perform dermal assessments daily at home.
- m. AEs will be collected starting from the first administered dose.
- n. Historical X-rays done within one year prior to the Screening Visit are acceptable. If subject does NOT have any X-Ray done within the past year, a mandatory new X-Ray to confirm the disease will have to be performed prior to starting the Washout Period.
- o. Only for rescue medication.

Note: [REDACTED] should be administered at the Screening and Baseline Visits after the subject has been consented and passed all the eligibility criteria defined in the protocol first.

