[REDACTED]

Listing 16.2.7.2
Serious Adverse Events
Safety Analysis Set

{Programming Note: Repeat listing 16.2.7.1, constrain to only serious adverse events}

Listing 16.2.7.3
Adverse Events Leading to Withdrawal
Safety Analysis Set

{Programming Note: Repeat listing 16.2.7.1, constrain to only adverse events leading to ET}

Listing 16.2.7.4
Listing of Deaths
Safety Analysis Set

{Programming Note: Repeat listing 16.2.7.1, constrain to only adverse events with fatal outcome}

Statistical Analysis Plan,
 Sponsor Noven Pharmaceuticals, Inc.
 Protocol Number HP-5000-US-05
 [REDACTED]

Noven Pharmaceuticals, Inc.
 Protocol HP-5000-US-05

Page 1 of x
 FINAL

Listing 16.2.8.1
Clinical Chemistry
Safety Analysis Set

Actual Treatment: XXXXXXX

Subject ID	Laboratory	Test	Visit	Collection Date	Sample Collected?	Test Result	Units	Standard Reference Range		Change from Baseline	Testing Conditions Met?
								Low	High		
XXXXX	xxxxxxxxxxxx	Baseline Week 4		DDMMYYYY	Yes	xxxxx	xxxxx	xx	xx	xxx	Yes
				DDMMYYYY	Yes	xxxxx*	xxxx	xx	xx		Yes
	xxxxxxxxxxxx	Baseline Week 4		DDMMYYYY	Yes	xxxxx^	xxxxx	xx	xx	xxx	Yes
				DDMMYYYY	Yes	xxxxx	xxxx	xx	xx		Yes
	xxxxxxxxxxxx	Baseline Week 4		DDMMYYYY	Yes	xxxxx	xxxxx	xx	xx	xxx	Yes
				DDMMYYYY	Yes	xxxxx	xxxx	xx	xx		Yes

Note: ^ = above normal range, * = below normal range. Treatment arms: HP-5000-[REDACTED] topical patch, HP-5000-[REDACTED] topical patch, and Placebo. T:\Noven\HP-5000-US-05\...\xxxxxx.sas run on DDMMYYYY at HH:MM for data extracted on DDMMYYYY, on SAS v9.4

Statistical Analysis Plan,
Sponsor Noven Pharmaceuticals, Inc.
Protocol Number HP-5000-US-05
[REDACTED]

Listing 16.2.8.2
Hematology
Safety Analysis Set

{Programming Note: Repeat listing 16.2.8.1}

Listing 16.2.8.3
Urinalysis
Safety Analysis Set

{Programming Note: Repeat listing 16.2.8.1}

Listing 16.2.8.4
Pregnancy Test
Safety Analysis Set

{Programming Note: Repeat listing 16.2.8.1, drop low/high/flag/change from baseline columns}

Statistical Analysis Plan,
 Sponsor Noven Pharmaceuticals, Inc.
 Protocol Number HP-5000-US-05
 [REDACTED]

Noven Pharmaceuticals, Inc.
 Protocol HP-5000-US-05

Page 1 of x
 FINAL

Listing 16.2.8.5
 Drug Screen
 Safety Analysis Set

Actual Treatment: XXXXXXX

Subject ID	Sample Type	Sample collected?	Reason not performed	Visit	Collection Date	Test Result
XXXXX	xxxxxxxxxxxx	Yes		Baseline	DDMMYYYY	xxxxx
XXXXX	xxxxxxxxxxxx	No	xxxxxxxxxxxxxxxx	Baseline	DDMMYYYY	xxxxx
XXXXX	xxxxxxxxxxxx	Yes		Baseline	DDMMYYYY	xxxxx

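### The SAP baseline rule ignores fasting status, so for glucose and lipids an unfasted Baseline-visit value can displace a fasted Screening value (minor)

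*SAP*

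**What the plan says.** **Fasting instruction.** Footnote g in Protocol Section 17.1, repeated under SAP Table 1, has two sentences. The first is general: "Fasting glucose and lipids should be performed after 8 to 10 hours of fasting". The second tells the site to instruct the subject to fast "before coming for the Baseline assessments, if not done at Screening".

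**Sampling.** The schedule marks the fasting glucose and lipids row at Screening, Baseline and Day 28. Protocol Section 10.1.2 lists laboratory blood sampling at the Baseline Visit without an exemption. Protocol Section 10.2.2.1.1 places these analytes inside the serum chemistry panel: "fasting glucose and total lipids [8 to 10 hours after fasting is required for these laboratory testing], cholesterol, triglycerides".

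**Endpoint.** Protocol Section 13.1.3 names the safety endpoint as "Change from Baseline in clinical laboratory results (including fasting glucose and total lipids", with fasting required. SAP Section 2.2.3 says the same.

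**Baseline rule.** SAP Section 5.1.1 reads: "The last non-missing observation recorded on or prior to the first patch application of study drug will be used as the baseline observation". It adds: "Typically, baseline will be the value recorded on the Baseline visit (Randomization". Fasting status plays no part in it.

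**Tabulation.** SAP Section 8.2 summarises change from baseline and low/normal/high shifts for each analyte. It does not restrict them to fasted samples.

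**The concern.** The footnote accepts a fasting result from either Screening or Baseline. The baseline rule always prefers the later visit. Where the fasting result came from Screening and the subject then arrived at Baseline having eaten, the plan discards the value that meets its own fasting requirement and keeps one that does not.

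An unfasted baseline set against a fasted Day 28 value makes glucose and triglycerides appear to fall on treatment. In the shift table it can turn a stable normal result into a High-to-Normal entry, or show a true Normal-to-High rise as High-to-High. The endpoint is labelled as a fasting change, and for those subjects it would not be one.

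**Working it through.** The plan states no figure on this point to reproduce. The check sets the rules side by side and then uses algebra for the size.

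**Step 1. Can a subject attend Baseline unfasted?** The only visit-specific fasting instruction is for Baseline, and it applies only if the thing in question was not done at Screening. A subject who met the condition at Screening therefore has no explicit instruction to fast again. The footnote's first sentence, read alone, still requires fasting whenever these tests are run. The two sentences do not fit together cleanly.

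**Step 2. Would a glucose or lipid value exist at Baseline for that subject?** The schedule marks the row at Baseline, the visit procedures list a blood draw with no exception, and the chemistry panel contains the analytes. Nothing states that they are omitted for subjects already tested fasted at Screening.

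**Step 3. Which value becomes baseline?** If a Baseline-visit value exists, it is the last non-missing pre-dose value and SAP Section 5.1.1 selects it. If none exists, the Screening value carries forward and no mismatch arises.

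**Step 4. Does another rule catch it?** The repeat-test rule in SAP Section 5.1.7 concerns repeats of a missing or invalid result. It does not class an unfasted sample as invalid, and it does not choose between two scheduled visits. Listing 16.2.8.1 has a column headed "Testing Conditions Met", but no derivation or summary table uses it, and the shell does not say which conditions it records.

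**Step 5. Is Day 28 fasted?** No instruction is written for that visit. Fasting there follows from the general sentence of footnote g and from the endpoint text.

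**Step 6. Size.** Let f be the fraction of an arm whose selected baseline is unfasted, and d the mean fed-minus-fasted difference for the analyte.

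- Selected baseline mean = fasted baseline mean + f × d.
- Mean change = Day 28 mean - (fasted baseline mean + f × d) = true mean change - f × d.
- At f = 0 the shift is 0. At f = 1 it is -d. Neither f nor d is in the documents, so this whole range is the result.
- Difference from placebo: the shift is -(f_active - f_placebo) × d. Whether a subject fasted before Screening or Baseline is settled before randomisation, so f has the same expectation in each arm and this term has expectation 0.
- Variance: if unfasted status is independent of the individual fed-minus-fasted difference (variance s²) and of the true change, the added variance is f × s² + f × (1 - f) × d². This is zero only when f = 0 or when there is no fed-fasted difference.

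**The case against.** The strongest reply is that footnote g has a harmless reading. What is done at Screening may be the fasting test itself, so that one fasted pre-dose result is obtained at Screening or, failing that, at Baseline. The schedule gives fasting glucose and lipids a row separate from the general laboratory row, which fits. On that reading there is no second value at Baseline, and SAP Section 5.1.1 correctly picks the fasted Screening result. This stands as a possible reading. The schedule mark at Baseline, the unconditional draw and the panel contents point the other way, so the text leaves it open.

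Second, f may be small. Protocol Section 10 requires consent before any study procedure, and consent and the laboratory draw both fall at the Screening Visit, so the documents describe no study-directed fast beforehand. Subjects not fasted at Screening are told to fast for Baseline, and their baseline is sound. This stands too. A reader might infer that most subjects would have an unfasted baseline, or attach a figure in mg/dL to the spurious fall. The documents support neither.

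Third, laboratory safety is descriptive, with no formal inference (Protocol Section 13.4.4, SAP Section 8), and a concurrent placebo arm would show the same displacement. That stands for mean changes. It does not fully rescue the shift table, where a baseline misclassified as High can mask a true rise in an individual.

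Fourth, SAP Section 5.1.7 might let an unfasted sample be marked invalid. The SAP does not say so, and the rule would still act only on repeats.

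**Conclusion.** The point holds as a gap in the rules. Footnote g can be read to let a subject who fasted at Screening attend Baseline unfasted, and SAP Section 5.1.1 would then use the unfasted value. It has effect only if glucose and lipids are actually measured at Baseline in such subjects, some of them are unfasted, and Day 28 is fasted as the general rule implies.

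The within-arm mean change is displaced by -f × d, anywhere from 0 to -d, with f possibly small or zero. Variance rises if f is above zero and the fed-fasted difference is not zero. A reader might infer that the comparison with placebo is biased; for the mean difference it is not, in expectation. Efficacy and all other analytes are untouched. The point is minor and held with moderate confidence, because the wording of the footnote allows a reading under which nothing goes wrong.

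**What to change.** Add to SAP Section 5.1.1 that, for glucose and lipid parameters, baseline is the last pre-dose value recorded as fasted, whether from the Screening or the Baseline Visit. Add that post-baseline values recorded as unfasted are listed but left out of the change-from-baseline and shift tables (the glucose and lipid rows of Tables 14.3.2.1.1 and 14.3.2.2.1).

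Use the "Testing Conditions Met" field for this once the sponsor confirms that it records fasting status. If it does not, another recorded source of fasting status is needed.

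Reconcile the two sentences of footnote g in both documents. State whether the tests are repeated at Baseline after a fasted Screening result and, if so, whether fasting applies.

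The cost is two sentences in the SAP, one programming filter and a clarified footnote. Subjects with no fasted pre-dose or no fasted post-baseline value drop out of these parameters only. If every sample was fasted and is recorded as such, no result changes.

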5.1.2. Adjustments for Covariates

Additional covariates for exploration include BMI, and Gender which may be added to analyses beyond baseline covariate factors, and will be noted in table outputs as appropriate. Further exploration of additional covariates will be considered as data becomes available and may

AD-ST-33.04 Effective date: 30-Jun-2017

include subgroups described in section [5.1.8](#).

5.1.3. Multiple Comparisons/Multiplicity

There will be no adjustments for multiple comparisons for efficacy or safety endpoints.

5.1.4. Handling of Dropouts or Missing Data

Missing endpoint values in this study may result from patients discontinuing from the study prematurely or missing intermediate assessments while remaining on study. For primary analysis of the primary endpoint and other efficacy endpoints missing observations will not be imputed. The primary analysis method for continuous endpoints will be based on a mixed model with repeated measures (MMRM) which utilizes all available data (complete and partial) from subjects included in an analysis set. The MMRM-based approach assumes that data are missing at random (MAR). MAR refers to a missingness mechanism that is independent of missing responses, conditionally on observed response history and covariates. This assumption inherently implies that the treatment effect is similar for those who discontinue prematurely and for those who complete the study in their respective treatment arms.

Sensitivity analyses to investigate robustness to missing data will be performed for the primary endpoint as described in Section [7.1](#)

Missing safety data including dermal evaluations will not be imputed.

5.1.5. Analysis Visit Windows

In general, analysis of all variables for this study will use the nominal visit or time point as collected in the CRF/database. Scheduled visits will be selected over unscheduled visits. Unscheduled visits will be presented in data listings. Only dermal evaluation data from unscheduled visits will be included into the summary tables.

5.1.6. Derived Variables

- Study Day = Assessment Date – Date of First Dose + 1
- Change from Baseline = Value Post-Baseline – Value at Baseline
- % Change from Baseline = $100 * \text{Change from Baseline} / \text{Value at Baseline}$
- WOMAC LK3.1 OA Sub-Index Pain = Range from 0 to 20 by summing each item relating to Pain (Walking, Stair climbing, Nocturnal, Rest, and Weight bearing) on a scale of 0 to 4, with 0 being no difficulty and 4 being extreme difficulty.

- WOMAC LK3.1 OA Sub-Index Stiffness = Range from 0 to 8 by summing each item relating to Stiffness (Morning Stiffness, and Stiffness occurring later in the day) on a scale of 0 to 4, with 0 being no difficulty and 4 being extreme difficulty.
- WOMAC LK3.1 OA Sub-Index Physical Function = Range from 0 to 68 by summing each item relating to Physical Function (Descending stairs, Ascending stairs, Rising from sitting, Standing, Bending to floor, Walking on a flat surface, Getting in/getting out of car, Going shopping, Putting on socks, Lying in bed, Taking off socks, Rising from bed, Getting in/out of bath, Sitting, Getting on/off toilet, Heavy domestic duties, Light domestic duties) on a scale of 0 to 4, with 0 being no difficulty and 4 being extreme difficulty.
- [REDACTED] and then dividing by [REDACTED] Higher scores on the WOMAC indicate worse pain, stiffness, and functional limitations.
- NRS Pain Score Average = Average of NRS pain scores for target and non-target knee reported for pain over the last 24 hours for the last 3 days prior to each clinic or phone visit except Screening Visit. The NRS pain scores in at least 2 of the last 3 days prior to washout start (Phone Visit 1) and Baseline is required. NRS is an 11-point scale from 0 to 10 where 0 = no pain and 10 = the worst pain imaginable.
- NRS Pain Score Worst = Worst NRS pain score for target and non-target knee reported for pain over the last 24 hours for the last 3 days prior to each clinic or phone visit except Screening Visit.

It is expected additional derived variables will be needed, but the SAP will not be amended unless they are part of the primary or secondary endpoints in the study.

5.1.7. Data Adjustments/Handling/Conventions

All collected data will be presented in listings. Data not subject to analysis according to this plan will not appear in any tables or graphs but will be included only in the data listings.

In general, for quantitative laboratory values reported as '<' or '<=' the lower limit of quantitation (LLOQ) or limit of detection (LOD), one-half of the reported value (i.e., LLOQ, LOD) will be used for analysis. For quantitative laboratory values reported as '>' or '>=' the upper limit of quantitation (ULOQ), the reported value (i.e., ULOQ) will be used for analysis.

For analysis purposes, repeat laboratory test results will not be used unless the original laboratory value is missing or indicated as invalid, in which case the first non-missing repeat laboratory value will be used for data analysis.

Adverse events will be coded using the MedDRA version 19.0 thesaurus. Concomitant and Prior medications will be coded using WHO Drug Dictionary (WHO-DD) version 2017.

If partial dates occur for AEs or medications, the convention for replacing missing dates for analyses is as follows:

For partial start dates:

- If the year is unknown, then do not impute the date but assign a missing value.
- If the month is unknown, then:
 - If the year matches the year of the randomization date, then impute the month and day of the randomization date.
 - Otherwise, assign 01 January
- If the day is unknown, then:
 - If the month and year match the month and year of the randomization date, then impute the day of the first study drug administration date.
 - Otherwise, assign 01.

For partial end dates:

- If the year is unknown, then do not impute the date but assign a missing value.
- If the month is unknown, then assign the last day of the year 31 December.
- If the day is unknown, then assign the last day of the month.

After implementing the rules above, to determine whether AEs (or medications) with missing start or stop dates are pretreatment or on/after treatment, the following strategy will be used:

1. If the start date and stop date are both missing, then the most conservative approach is taken and the AE (or medication) is considered to be treatment emergent (or concomitant).
2. If the start date is missing but the stop date is not missing and is after the day of study drug administration, then the most conservative approach is taken and the AE (or medication) is considered to be treatment emergent (or concomitant).
3. If the start date is missing but the stop date is not missing and is on or before the day of study drug administration and after the date of signed informed consent, then the AE (or medication) is considered to be before treatment (or prior).

If the start date is not missing but the stop date is missing, then the most conservative approach is taken and medication is considered to be concomitant while the AE is defined by start date.

A treatment related AE is any AE with a relationship to the study drug of “Possibly Related” or “Definitely Related”. Any AE with a missing relationship will be analyzed as treatment related. If an AE has a missing severity, it will be imputed as “Severe”.

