10.1.2 Baseline Visit (Visit 2, Day 0)

The following will take place during the Baseline Visit (Visit 2, Day 0):

1. Confirm subject's continued eligibility relative to inclusion/exclusion criteria.
2. Assign a subject ID number and randomly assign the subject to a treatment group using IVRS.

3. Obtain vital sign measurements, including weight.
4. Administer the WOMAC questionnaire.
5. Perform Patient's Global Assessment (PGA).
6. Perform an NRS 11-point pain assessment for the target knee and non-target knee pain.
7. Review subject's use of rescue medication.
8. Perform a 12-lead ECG.
9. Obtain blood and urine samples for laboratory testing.
10. Perform a urine drug, alcohol and pregnancy tests.
11. Review the subject's eDiary.
12. Perform Baseline dermal safety assessment (irritation only).
13. Review subject's use of prior/concomitant medications.
14. Dispense rescue medication and perform rescue medication accountability/reconciliation.
15. Dispense the Double-blind study drug and instruct subjects on proper patch application.
Subjects should apply the patch at home the next day after showering/bathing.
16. Subjects will be instructed not to bathe or shower while wearing the study drug; a bath or a shower may be taken in the morning or in the evening before any patch is applied [REDACTED].
17. Subject will be instructed to report to the site and record on the eDiary patch detachment and incidences of irritation, discomfort, and adhesive residue and not to participate in strenuous activities or other activities that cause heavy perspiration during the double-blind treatment phase.

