6.6. Concomitant Medications

Concomitant medications will be listed similarly to Prior medications. A concomitant medication is any non-protocol specified drug or substance administered during participation in the study on or after first date of study drug. A medication can be considered both concomitant and prior if the subject took medication prior to the study and continued taking it after first study drug administration.

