8.1. Adverse Events

All adverse events collected are treatment-emergent adverse events (TEAEs) since only AEs after treatment start are collected. All AEs, and SAEs will be coded using the MedDRA version 19.0 thesaurus.

The frequency and percentage of subjects reporting AEs, grouped by MedDRA system organ class and preferred term, will be tabulated by severity and treatment group for the SAF. Such summaries will be displayed for AEs, SAEs, AEs by relationship to study drug, and AEs by severity.

In the case of multiple occurrences of the same AE within the same subject, each subject will only be counted once for each preferred term. In the summaries showing severity and relationship to study medication the event with the maximum severity or strongest relationship will be reported. If a particular event is missing the severity and/or relationship, then the strongest possible severity or relationship will be assumed for analysis (severity = severe, relationship = definitely related).

Missing and partially missing AE start and/or stop dates will be imputed for the purpose of statistical analysis, according to the specifications described in Section [5.1.8](#).

In the AE data listings, all AEs will be displayed.

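### SAP 5.1.7's partial-date rules can date an on-treatment adverse event to the day before the first patch, and can start a medication after its own recorded stop

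*SAP*

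**What the plan says.** SAP 5.1.7 applies one set of start-date rules to adverse events and medications.

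- **Month unknown:** "If the year matches the year of the randomization date, then impute the month and day of the randomization date". In any other year the date becomes 01 January.
- **Day unknown, in the month and year of randomisation:** "then impute the day of the first study drug administration date". In any other month the day becomes the first.
- **End dates** are completed separately. For example: "If the day is unknown, then assign the last day of the month". No rule compares a start with a stop.

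Classification steps follow, but they cover only records whose start or stop is still missing after imputation. Among them, if the start is present and the stop is missing, a medication is taken as concomitant and an adverse event is classified by its start date.

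SAP 6.5 defines a prior medication as one administered before the first study drug date. SAP 6.6 says: "A concomitant medication is any non-protocol specified drug or substance administered during participation in the study on or after first date of study drug". SAP 8.1 says: "All adverse events collected are treatment-emergent adverse events (TEAEs) since only AEs after treatment start are collected".

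On timing, Protocol 10.1.2 places randomisation at the Baseline Visit, Day 0: "Assign a subject ID number and randomly assign the subject to a treatment group using IVRS". It then says: "Subjects should apply the patch at home the next day after showering/bathing". The notes to the schedule in Protocol 17.1 agree: "Study treatment will be applied on Day 1 of the Double-blind Treatment Phase".

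**The concern.** The two start-date rules differ by one day, and that day separates before treatment from on treatment. An adverse event can be collected only after the first patch, so a rule that moves it to Day 0 gives it a date outside the collection period. For an event with no stop date, 5.1.7 then makes it pretreatment while 8.1 makes it treatment-emergent.

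For medications the gap is the missing check against the stop date. The design makes this likely to arise, because subjects must be on an NSAID before Screening and must stop analgesics at washout. Such records have a recorded stop before Day 0 and often a vague start. At stake are the start date, study day, duration and prior/concomitant status shown in Listings 16.2.7.1 (adverse events) and 16.2.4.3 (medications).

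**Working it through.** **Inputs.** Randomisation is Day 0 and the first patch Day 1 (Protocol 10.1.2 and 17.1). SAP 5.1.6 gives Study Day = assessment date − first dose date + 1. The start rules are those of SAP 5.1.7 and the medication definitions those of 6.5 and 6.6. The plan states no figure to reproduce. The calendar dates below are an illustration: randomised 15 March 2018, first patch 16 March 2018.

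| Record | Rule | Imputed start | Result |
|---|---|---|---|
| Adverse event, start 2018 | month unknown | 15 March | Study Day = 15 − 16 + 1 = 0 |
| Adverse event, start March 2018 | day unknown | 16 March | Study Day = 16 − 16 + 1 = 1 |
| Drug, start 2018, stop 1 March | month unknown | 15 March | 15 − 1 = 14 days after its stop; before 16 March, so prior |
| Drug, start March 2018, stop 10 March | day unknown | 16 March | 16 − 10 = 6 days after its stop; by start date concomitant, by stop date not |

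**Every randomisation date in 2018.** The rules were also applied literally to all 365 randomisation dates, with the first patch one day later.

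- *Adverse events with true onset on Days 1 to 35:* 365 × 35 = 12,775 cases. With the month unknown, 12,145 have their onset in the randomisation year, and all 12,145 get Study Day 0. The other 630 fall in the next year, and 01 January is never before the first patch. With only the day unknown, none of the 12,775 falls before the first patch.
- *Drugs started up to 60 days before the first patch and stopped before it, month unknown, same year:* 575,840 of 595,970 get a start after their stop. The remaining 20,130 stopped on Day 0 itself, so start equals stop. None of the 595,970 is concomitant by start date.
- *The same, day unknown, started in the randomisation month:* 56,354 of 62,092 get the first-patch date, which is after their stop and concomitant by start date. The remaining 5,738 belong to subjects randomised on the last day of a month. Their first-patch day number is 1, so the imputed start is the first of the randomisation month.

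These counts show how mechanically the rules act. They are not expected frequencies in the trial.

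**Do the later steps rescue these records?** No. A record with an imputed start and a known stop no longer has a missing date, so the classification steps do not reach it and it falls back on 6.5 and 6.6.

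**The case against.** The strongest reply is that little follows from any of this. SAP 8.1 counts every collected adverse event as treatment-emergent. Imputation is for analysis, while listings show collected data, so at most a derived study day or duration is off. An adverse event with an unknown month should be rare in a 4-week trial with clinic visits at Days 7, 14 and 28 and daily diaries. SAP 6.6 speaks of when a drug was administered, and a drug stopped on 10 March was not administered on 16 March. All of this stands and limits the size of the point. It does not remove a rule that produces a start after its own stop, and the SAP does not say which date decides prior or concomitant status.

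A reader might infer four larger harms. The documents do not support them.

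- *The unknown-month rule makes washed-out drugs concomitant.* It gives Day 0, which is before the first patch, so by start date they stay prior.
- *The NSAID that qualified the subject will look like prohibited use on treatment.* It needs 30 days of use before Screening, then 3 days to washout and at least 7 days of washout. Its start is at least 30 + 3 + 7 = 40 days before Day 0 and cannot be in the randomisation month, so the unknown-day rule never applies to it.
- *Tables 14.1.3 and 14.1.5 will lose records.* SAP 6.7 builds the previous-treatment summaries from the medication eCRF page and does not mention the prior flag.
- *NSAID durations in the 5.1.8 subgroups will be zero or negative.* SAP 5.1.8 gives no duration formula. The subgroups are optional and their categories are still to be confirmed.

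**Conclusion.** The point holds as a small wrong-as-written rule in SAP 5.1.7. The adverse event part is certain on a literal reading when the onset year is the randomisation year and the first patch goes on the day after randomisation, as the protocol instructs. The contradiction with 8.1 arises only when the stop date is also missing. The start-after-stop part is equally certain under the unknown-month rule for drugs stopped before Day 0. Under the unknown-day rule it needs the drug to have started and stopped in the randomisation month before the first patch, with randomisation not on the month's last day. The concomitant flag needs those same conditions and classification by start date alone, so it can happen but is not assured.

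The effect stays within derived study day, duration and prior/concomitant flags in the listings. The documents do not give the number of partial dates. It is probably small for adverse events and larger for start dates of long-used drugs.

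**What to change.** Amend SAP 5.1.7 before database lock:

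1. For adverse event starts, use the first study drug date as the anchor in both the unknown-month and unknown-day rules.
2. Never impute an adverse event or medication start later than a recorded stop date. Where the stop is itself partial, compare with the stop as completed by the end-date rule.
3. State that a medication with a recorded stop before the first study drug date is prior only.

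In the example, the year-only adverse event moves to 16 March (Study Day 1). The two drugs get starts of 1 March and 10 March, and both are prior only. While editing, correct the cross-reference in 8.1, which points to 5.1.8 for the date rules.

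The cost is three sentences and a small program change. The cap makes dates coherent, not accurate: a drug capped at its stop still shows an artificially short use, so duration of use should not be calculated from imputed starts. Sending every year-only medication start to 01 January is not recommended. It would backdate drugs that truly began on treatment and mark them as prior as well.
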